9.1.16 Adverse Events

Information regarding occurrence of AEs will be captured from randomization through Visit 3. Duration (start and end dates), grade, seriousness, outcome, treatment, and relation to study arm treatment will be recorded on the case report form (CRF).

In addition, any overnight admissions to the hospital that occur between randomization and Visit 3 will be captured on the CRF.

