14.3 Analysis of Secondary Endpoints

Differences between treatment arms will be estimated within each study for i) subjects initiating acute antibiotics, ii) subjects hospitalized, iii) subjects with a pulmonary exacerbation, and iv) subjects who meet adherence criteria. These differences will be estimated using logistic regression methods and reported with confidence intervals accounting for randomization strata.

Differences in the between treatment arms from randomization to week 6 will be estimated in each trial for i) CRISS, ii) CFQR, and iii) LCI using general linear regression adjusting for randomization strata. Change in FEV₁ % predicted from Screening to randomization will also be compared between treatment arms within each study using linear regression adjusting for randomization strata. Descriptive summaries of the change from Screening to randomization, and randomization to week 2 will also be provided for all continuous endpoints.

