14.4 Analysis of Safety Endpoints

All reported SAEs and AEs will be coded using MedDRA and grouped by body system. SAEs and AEs will be tabulated by treatment arm using standard coding terms sorted by body system. The incidence of AEs in each treatment arm will be tabulated by seriousness, severity, and relationship to treatment arm assignment. If an AE is reported more than once during the study period for a given subject, the greatest severity and the worst-case relationship will be presented in tables.

The number of SAEs and AEs will be summarized for each treatment arm as follows: (i) The proportion of subjects with at least one (S)AE, (ii) The average number of (S)AEs per subject, and (iii) The rate of (S)AEs per subject week of follow-up. Histograms showing the frequency of the number of (S)AEs in each treatment group will be included. Rates of (S)AEs by System Organ Class (SOC) will be presented by treatment group. Poisson regression modeling will be used to derive rate ratios and 95% CIs for each SOC. The rate ratios will be compared using a two-sided 0.05 level test for Poisson count data.

In addition to AEs, the proportion of subjects temporarily or permanently changing their assigned therapy will be summarized.

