3.2.5. Hospitalizations and Pulmonary Function Decline

The number of hospitalizations is summarized within each intervention arm as follows: (i) The proportion of participants with at least one hospitalization, (ii) The average number of hospitalizations per participant, (iii) The rate of hospitalizations per participant week of follow-up, and (iv) The number of days hospitalized per participant. Poisson regression modeling is used to

derive rate ratios and 95% confidence intervals. Rates by arm are compared using a two-sided 0.05 level test for Poisson count data. Proportions of participants with at least one hospitalization are also compared between arms with estimated differences and corresponding 95% confidence intervals by the Newcombe-Wilson method without continuity correction; p-values are from a two-sided 0.05 level Fisher's Exact test. The difference between intervention arms in participants hospitalized is estimated using logistic regression methods and reported with confidence intervals accounting for randomization strata.

The proportions of participants with a significant decline in FEV₁ % predicted from Week 0 are also summarized by intervention arm.

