3.2.8. Exacerbation and Concomitant Medication Parameters

The number of protocol-defined and physician identified pulmonary exacerbations (PEX) experienced by participants from Week 0 (Visit 1) to Week 6 (Visit 3) are summarized by intervention arm as follows: (i) The total number of PEX, (ii) The rate of PEX per participant week of follow-up, (iii) The average number of PEX per participant, (iv) The proportion of participants with at least one PEX, and (v) the total requiring antibiotics (acute IV, oral, or inhaled) or hospitalization. Poisson regression modeling is used to derive rate ratios and 95% confidence intervals. Rates by arm are compared using a two-sided 0.05 level test for Poisson count data. Proportions of participants with at least pulmonary exacerbation are also compared between arms with estimated differences and corresponding 95% confidence intervals by the Newcombe-

Wilson method without continuity correction; p-values are from a two-sided 0.05 level Fisher's Exact test.

Also summarized is the frequency of signs and symptoms for protocol-defined PEx for each intervention arm and overall. The difference between intervention arms in participants experiencing a protocol-defined PEx is estimated using logistic regression methods and reported with confidence intervals accounting for randomization strata.

The difference between intervention arms in participants initiating acute antibiotics is estimated using logistic regression methods and reported with confidence intervals accounting for randomization strata.

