Number (%) of participants with at least one Respiratory AE		Prop. Diff (95% CI) [3]
FEV ₁ (% predicted) >=90 to <100%, n (%)		
Total follow-up (weeks)		
Total number of Respiratory AEs		
Respiratory AE rate [1]		Rate Ratio (95% CI) [2]
Avg. number of Respiratory AEs per person		
Number (%) of participants with at least one Respiratory AE		Prop. Diff (95% CI) [3]
FEV ₁ (% predicted) >=100%, n (%)		
Total follow-up (weeks)		
Total number of Respiratory AEs		
Respiratory AE rate [1]		Rate Ratio (95% CI) [2]
Avg. number of Respiratory AEs per person		
Number (%) of participants with at least one Respiratory AE		Prop. Diff (95% CI) [3]

[1] The rate of occurrence is equal to the number of events divided by the total number of follow-up weeks in each intervention arm for the corresponding FEV₁ (% predicted) subgroup.

[2] Poisson regression is used to calculate the rate ratio and corresponding 95% CI. The ratio is STOP Taking / KEEP Taking.

[3] 95% confidence interval calculated using the Newcombe-Wilson method without continuity correction. The difference is STOP Taking - KEEP Taking.

5 Hospitalizations and Pulmonary Function Decline

Table 5.1. Overview of Hospitalizations (ITT population)

This table presents the number of participants hospitalized, number of hospitalization events, and the number of days hospitalized between Week 0 (Visit 1) and the end of follow-up.

	STOP Taking (N=)	KEEP Taking (N=)	Total (N=)	P-value [Final Report only]
Hospitalizations Events				
Number of Hospitalization Events per Patient: N (%)				
At least one				Difference (95% CI) [2] p-value [2]
0				
1				
2				
3				
Total Number of Hospital Events				
Mean number of Events/Participant				
Rate per Week [1]				Rate Ratio (95% CI) [3] p-value [3]
Hospitalization Days				
Mean Number of Days Hospitalized per Patient (SD)				
				Rate Ratio (95% CI) [3] p-value [3]
Median				
Min, Max				

[1] The rate per week is calculated as the total number of hospitalization events divided by the total weeks of follow up for each intervention arm. The total number of follow-up weeks in STOP taking intervention arm is X and in KEEP taking intervention arm is X.

[2] 95% confidence interval for the difference in proportions is calculated using the Newcombe-Wilson method without continuity correction. The p-value is obtained from the Fisher's exact test. The difference is STOP Taking – KEEP Taking.

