[3] Poisson regression is used to calculate the rate ratio, corresponding 95% CI and p-value. The ratio is STOP Taking / KEEP Taking.

Table 5.2. Logistic Regression Model Results for Odds of Participant Hospitalization (ITT population)

This table summarizes the estimate (as odds ratio) comparing the proportion of participants hospitalized between intervention arms from Week 0 (Visit 1) to Week 6 (Visit 3) using a logistic regression model. Each participant is only counted once in the model (i.e., outcome is 1 if participant was hospitalized at least once between Week 0 and Week 6. Otherwise, outcome is 0). The models summarized are for an unadjusted model and one that adjusts for the randomization strata: (Week 0 FEV₁ % Predicted (≥90% or <90%), therapy combination at screening (single or concurrent use of hypertonic saline and/or dornase alfa), prior study enrollment (yes or no), and Week 0 age (≥18 years or < 18 years)).

Model Covariates		STOP Taking Proportion Estimate (N =)	KEEP Taking Proportion Estimate (N =)	Odds Ratio (95% CI)	P-value
Model Unadjusted					
Intervention Arm:	STOP Taking hypertonic saline [1]				
Model Adjusted for Randomization Strata					
Intervention Arm:	STOP Taking hypertonic saline [1]				
Randomization Strata:	FEV ₁ % Predicted ≥90% [2] On both HS and Dnase [3] Prior study enrollment [4] Age ≥18 years [5]				

- [1] Compared to reference level, KEEP taking hypertonic saline.
- [2] Compared to reference level, FEV₁ % Predicted < 90% at Week 0 (Visit 1).
- [3] Compared to reference level, one therapy at Week -2 (Screening).
- [4] Compared to reference level, no prior study enrollment.
- [5] Compared to reference level, age <18 years at Week 0 (Visit 1).

Table 5.3. Summary of Pulmonary Function Decline (ITT population)

This table summarizes the proportion of randomized participants with a significant decline in FEV₁ % Predicted from Week 0 (Visit 1).

	STOP Taking (N=x)	KEEP Taking (N=x)	Difference (95% CI) [2]
Number of Participants With FEV₁ Measure Completed			
At Either Week 2 or Week 6, N			
At Week 2, N			
At Week 6, N			
≥ 5% Decline in FEV₁ % Predicted from Week 0 [1]			
Number of Participants at Week 2 or Week 6, n (%)			Difference (95% CI)
Number of Participants at Week 2, n (%)			Difference (95% CI)
Number of Participants at Week 6, n (%)			Difference (95% CI)
≥ 10% Decline in FEV₁ % Predicted from Week 0 [1]			
Number of Participants at Week 2 or Week 6, n (%)			Difference (95% CI)

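### SAP Table 5.1 tests days in hospital with plain Poisson regression, which treats the days of one stay as independent events; the interval is too narrow unless each stay counts as one day.

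*SAP*

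**What the plan says.** SAP section 3.2.5 lists four hospitalization summaries, the last being "iv) The number of days hospitalized per participant". It then names Poisson regression for rate ratios and a two-sided 0.05 test for Poisson counts, without saying clearly whether this covers the days summary. The Table 5.1 shell settles it. Its Hospitalization Days block contains "Mean Number of Days Hospitalized per Patient (SD", and the analysis cell reads "Rate Ratio (95% CI) [3] p-value [3". Footnote 3 reads "3] Poisson regression is used to calculate the rate ratio, corresponding 95% CI and p-value". No scale parameter, robust variance or other count model is named. The same footnote serves the event-rate row.

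What feeds the row is in Protocol section 9.1.16: "any overnight admissions to the hospital that occur between randomization and Visit 3 will be captured on the CRF". A stay may therefore last one night or many.

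The protocol prescribes no model for days. Its hospitalization endpoint (section 5.2) is the proportion hospitalized, and section 14.3 puts "ii) subjects hospitalized, iii) subjects with a pulmonary exacerbation" among the outcomes for logistic regression. Section 14.4 does prescribe Poisson for adverse events: "Poisson regression modeling will be used to derive rate ratios and 95% CIs for each SOC". Elsewhere in the SAP, the footnotes to Tables 8.1 and 8.2 specify quasi-Poisson for exacerbation rates.

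**The concern.** Poisson regression takes the variance of the count as equal to its mean. That is a workable approximation for separate admissions. It fails for days, because once a participant is admitted the days of that stay arrive together. The information lies in the number of stays, while the model counts the days. The standard error is then too small and the p-value too low.

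One or two long stays could produce a nominally significant difference in days, in either direction, in the same table whose participant-level Fisher test shows nothing. In a trial of whether stopping a therapy is safe, such a figure is easily quoted, and SAP section 2.3 applies no multiplicity adjustment.

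**Working it through.** **Inputs.** From the documents: about 200 participants per arm (Protocol 6.1), a 6-week study period and a two-sided 0.05 test (SAP 3.2.5). The plan gives no admission rate, length of stay or expected interval for this row, so there is no plan figure to reproduce. Assumed: 1%, 2%, 3% or 5% of participants have one stay, L is uniform over the ranges shown, and the arms do not differ.

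**Formula.** If a participant has a stay with probability p, lasting L days, then

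variance/mean of days = E[L²]/E[L] − p·E[L].

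The first term equals mean stay × (1 + CV²). Plain Poisson sets this ratio to 1, so the interval for the log rate ratio is too narrow by its square root.

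For stays uniform on 3–10 days:
- E[L] = 6.5 and E[L²] = 380/8 = 47.5, so E[L²]/E[L] = 7.31.
- Subtracting p·E[L], from 0.065 (p = 1%) to 0.325 (p = 5%), gives 7.24 to 6.98.
- The square root is 2.6–2.7.

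If all stays are equal the ratio is about L, so the factor is about 2 at 4 days and 3 at 9 days.

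**Simulation.** 40,000 trials per setting. Poisson test z = log(a/b)/√(1/a + 1/b), where a and b are total days per arm. Rejection rates are among trials with stays in both arms; ranges run over p = 1–5%.

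| Days per stay | Variance/mean | CI too narrow by | Rejections by the nominal 5% test |
|---|---|---|---|
| all 1 | 0.95–0.99 | 1.0 | 0.1–3.6% |
| 1–2 | 1.59–1.65 | 1.3 | 2–11% |
| all 2 | 1.90–1.98 | 1.4 | 4–15% |
| 1–3 | 2.23–2.31 | 1.5 | 7–18% |
| 2–5 | 3.68–3.82 | 1.9–2.0 | 19–31% |
| 3–10 | 6.98–7.24 | 2.6–2.7 | 37–46% |
| 7–14 | 10.5–10.9 | 3.2–3.3 | 47–55% |
| 10–14 | 11.6–12.0 | 3.4–3.5 | 49–58% |

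A separate calculation with Poisson-distributed numbers of stays (0.05 per participant) agrees. Plain Poisson rejected in 4.3% of trials with one-day stays, 17.1% with two-day stays and 45.6% with seven-day stays.

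**Example 1: one 14-day stay against one 4-day stay, 200 per arm.**
- Rate ratio 14/4 = 3.5; log 3.5 = 1.253; Poisson SE = √(1/14 + 1/4) = 0.567.
- Poisson: 95% CI 1.15–10.6, p = 0.027.
- Pearson dispersion 9.0, so the SE triples. Quasi-Poisson: 95% CI 0.12–99, p = 0.46.
- Fisher test on 1/200 against 1/200: p = 1.0.

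**Example 2: ten against five stays of 7 days each (70 v 35 days).**
- Plain Poisson on days: rate ratio 2.00, CI 1.33–3.00, p = 0.0008.
- Quasi-Poisson (dispersion 6.77): CI 0.70–5.75, p = 0.20.
- Poisson on the 10 v 5 stays: CI 0.68–5.85, p = 0.21. The quasi-Poisson result agrees with the evidence in the stays themselves.

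**Check of the remedy.** Quasi-Poisson with dispersion floored at 1 and a t reference on 398 df rejects in 0–4.1% of null trials across all these settings, and also for stays of 1–5 days, all 4 days and all 9 days. It is conservative when few are admitted: 0–0.2% at 1% admitted and 0.6–1.5% at 2%. At least one arm has no stays in 25% of trials at 1% admitted, 3.5% at 2%, 0.5% at 3% and under 0.01% at 5%.

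**The case against.** The strongest reply is that the size rests wholly on assumed inputs. Participants must be clinically stable at screening and randomization, so over six weeks admissions may be few. With 1% admitted, the plain Poisson test rejects only 2% of the time for stays of 1–2 days and 4% when all stays last 2 days, so the null is still covered at the nominal level. The rates above also condition on stays in both arms. For stays of 3–10 days at 1% admitted, counting the 25% of trials without such stays as non-rejections lowers 37% to about 28% (0.75 × 37%). This stands as a limit on the size. It does not rescue the model: the variance is still misstated, and the small rejection rates reflect very few stays.

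Second, the exact condition for safety is one counted day per stay. The documents do not say how days are counted; if one night counts as two calendar days, the factor is already about 1.4. Table 5.1 also allows for repeat stays, which could add further dispersion.

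Third, materiality is low. The table shows the SD, median and range of days, so a single long stay is visible beside the Fisher and Newcombe-Wilson results, and Table 5.2 gives the adjusted logistic analysis. No decision rule uses the days row. This stands and sets the severity.

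Fourth, a dispersion estimated from two to four stays is poor, so a descriptive row may be cleaner. That is fair, and the fix allows it.

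Finally, the SAP uses the term loosely: section 3.2.8 says "Poisson regression modeling is used to derive rate ratios and 95% confidence intervals" for exacerbations while Tables 8.1 and 8.2 say quasi-Poisson. A dispersion term may have been intended in Table 5.1 too. If so, footnote 3 should say so, which is the same edit.

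**Conclusion.** The concern holds, at low severity. As written, Table 5.1 fits plain Poisson regression to days in hospital, and the resulting interval is too narrow whenever stays contribute more than one counted day. The direction needs no outside data. The size does: under the assumptions above, the factor runs from 1.0 to 3.5 and null rejection from 0.1% to 58%.

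The finding is confined to the interval and p-value of one row. The rate ratio, the primary and excess-harm analyses, and the Fisher, Newcombe-Wilson and logistic analyses of hospitalization are unaffected. Adverse event, serious adverse event and hospitalization-event rates are not in question.

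**What to change.** For the Hospitalization Days row only, keep the rate ratio but obtain its interval and p-value from quasi-Poisson regression with the Pearson dispersion not allowed below 1. This is the type of model the SAP already names in Tables 8.1 and 8.2. If either arm has no stays, show the row descriptively, without a ratio or p-value. Making the row descriptive in all cases is an acceptable alternative, and attractive if few admissions are expected.

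State the choice in SAP section 3.2.5 and in a separate footnote to Table 5.1, before arm-level hospitalization data are seen. If interim reporting has already exposed such data to those making the change, the change record should say so.

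Leave adverse event, serious adverse event and hospitalization-event rates as planned. As a separate wording correction, align section 3.2.8 with the quasi-Poisson footnotes of Tables 8.1 and 8.2.

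The cost is one footnote, one sentence and minor programming. There is no departure from the protocol. The interval widens by the factors shown, and the test is conservative when few participants are admitted.
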